in a 12HR combination since both isoniazid and rifapentine can damage the liver; CDC is calling for studies of 12HR in prisoners, but have not yet funded research. In the absence of studies of 12HR use in prisoners, it is crucial to assess both completion rates and tolerability (especially when high HCV prevalence is present).

Eligibility for Part B includes:

- 1) Meets inclusion criteria for Part A
- 2) Has latent TB (HIV+, or TST \geq 10mm (HIV-)) and no active TB disease
- 3) \geq 6 months before end of sentence to ensure option for treatment completion
- 4) AST/ALT <5 ULN, or AST/ALT <3 x ULN if TBil >2 x ULN
- 5) Not on a protease inhibitor (drug interaction with rifapentine)
- 6) No known porphyria
- 7) Not pregnant (women only).

Enrolled participants will undergo block stratified randomization, stratifying on four factors: a) CD4 <350 (if HIV+); b) HCV Ab status; c) ART status; and d) opioid dependence. After randomization and allocation to 12HR or 26H, participants will be provided 12HR weekly (12 weeks) and 26H daily (26 weeks) as directly observed therapy. Every 4 weeks, patients will be monitored for AST/ALT, adverse side effects and pregnancy. Premature treatment discontinuation will occur for any DAIDS Grade 4 toxicity, patient refusal to continue, or pregnancy (women only).

Study Design: TB Studies

Legend: LTBI=latent TB infection; H=isoniazid; HP=isoniazid + rifapentine; MMT= methadone maintenance treatment; BPN/NLX= buprenorphine/naloxone; OAT=opioid agonist treatment; ART= antiretroviral therapy; HCV= hepatitis C virus.

Part C:

A two-arm **preference trial** (no MAT, and methadone) of prisoners with opioid use disorders who are not or are currently being treated for TB and/or HIV, and are about to transition to the community and need to continue their treatment post-release. Patients may or may not be returning to Klang Valley and within 25 km of our research site. We anticipate enrolling 25-50 participants per arm.

Once consented, study participants will be provided an informed decision-making aid that will help them decide if medication-assisted treatment, specifically Methadone, is best for them. Participants will also have the option not to enroll in medication-assisted treatment.

[figure not shown]
Informed decision-making aid:

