saturation of themes is reached. Participants will undergo informed consent prior to participating, and will be compensated 50RM for their time.

Upon making an informed decision using the SDM developed from the focus groups, those that choose methadone maintenance treatment (MMT) will initiate 5 mg of methadone, 3-4 months prior to release from prison. The dose will increase in 5 mg increments every 7 days (as tolerated) until the daily dose is escalated to at least 80 mg or optimal dose before the date of release. Patients prescribed MMT will receive medication daily in prison, and will receive their medications weekly in form of take-way dosing. MMT will be dispensed at the community research site. All participants will be maintained on medication-assisted treatment and will receive follow-up care for 6 months after release from prison.

After a baseline assessment, our research assistant (RA) would meet the participant at the prison on the day of release to undergo a brief assessment, urine testing and to introduce the patient to our community research site to ensure that s/he can find the site after release and take the participant home so that our research assistants can know where the person is living/residing. This process will also improve trust between the research staff and the participant. Thereafter, all participants will be seen monthly, where they will undergo urine screening and be assessed for alcohol and drug use using timeline follow-back (TLFB), appointments for HIV and/or TB, adherence to HIV and/or TB medications, assessments of legal, employment, family issues using the Lite version of the Addiction Severity Index (ASI), depressive symptoms, health-related quality of life (HRQoL), satisfaction with their treatment. They will also be assessed for diversion (and urine testing).

The primary outcome will be the proportion completing treatment for active or LTBI. Secondary analyses will compare Kaplan Meier curves using Cox proportion hazards and time to discontinuation. TB treatment adherence will also be measured using MEMS caps and analyzed as we have done previously in TB patients in Ukraine

Eligibility for Part C includes:

- 1) Meets inclusion for part A, if possible
- 2) Opioid dependence
- 3) Has LTBI or active TB disease (based on screening in Part A), or no TB
- 4) Returning to live in Kuala Lumpur/Klang Valley region (within 25 km of Kerinchi research site), if possible
- 5) ≤ 6 months before end of sentence

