- \geq 3 month prison sentence

1b inclusion:

- Meets inclusion criteria for part A
- Has latent TB (HIV+, or TST \geq 10mm (HIV-)) and no active TB disease
- >6 months before end of sentence to ensure option for treatment completion

- AST or ALT <5X ULN, or AST/ALT <3x ULN if TBil >2x ULN
- Not on a protease inhibitor (drug interaction with rifapentine)
- No known porphyria
- Able to provide informed consent

1c inclusion:

- Meets inclusion criteria for Part A, if possible
- Opioid dependence
- Has latent TB (HIV+, or TST \geq 10 mm (HIV-)), or active TB infection, or no TB
- Returning to live in Kuala Lumpur/Klang Valley region (within 25 km of Kerinchi research site), if possible
- AST/ALT <5X normal
- \leq 6 months remaining in prison
- Able to provide informed consent

Exclusion Criteria: Pregnant women or women planning to become pregnant will be excluded if we implement methadone or buprenorphine during pregnancy, the infant born to the mother is highly (>60%) likely to develop an infant abstinence syndrome that is avoidable by not providing MMT. If a woman becomes pregnant during the course of the study, MMT will not be discontinued if she is receiving it as withdrawal has resulted in pre-term labor. For women preferring not to be OAT, but who relapse to drug use, entry onto MMT will not be an exclusion criteria for remaining in the study.

8. How will **eligibility** be determined, and by whom?

Eligibility will be determined by the Research Assistants (RAs) hired by the University of Malaya – CERIA to work on this study. An eligibility screening form will be developed into REDCap, a data collection and management application that will be used by the local RAs.

Prior to enrollment, laboratory testing will be completed to ensure normal LFTs and urine testing will be completed to ensure that female participants are not pregnant.

9. **Risks:** Describe the reasonably foreseeable risks, including risks to subject privacy, discomforts, or inconveniences associated with subjects participating in the research.

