For patients in Aim 1, Part B (trial of 26H vs 12HR) and Part C (MMT, vs. no MAT), patients will be seen monthly clinically for symptoms of hepatitis or neuropathy and LFTs shall be monitored. Anyone whose LFTs increase to $>5X$ ULN, or $>3X$ ULN with symptoms of jaundice, nausea or fatigue, will be stopped from receiving medications and LFTs will be monitored weekly to ensure that LFTs are decreasing. Similarly, if patients develop Grade 3 or higher peripheral neuropathy, they will be discontinued. Of note, LFTs will be measured at baseline and monthly for 3 months for 12HR and monthly x 6 months for 26H.

MMT patients will be seen daily for the first month and may have their medications dispensed less frequently if they have no evidence of using illicit drugs by self-report or urine testing.

11. Data and Safety Monitoring Plan: Include an appropriate Data and Safety Monitoring Plan (DSMP) based on the investigator's risk assessment stated below. (Note: the HIC will make the final determination of the risk to subjects.) For more information, see the Instructions, page 24.

- a. What is the investigator's assessment of the overall risk level for subjects participating in this study?
- b. If children are involved, what is the investigator's assessment of the overall risk level for the children participating in this study?
- c. Include an appropriate Data and Safety Monitoring Plan. Examples of DSMPs are available here <http://www.yale.edu/hrpp/forms-templates/biomedical.html> for
 - i. Minimal risk
 - ii. Greater than minimal

Aim 1parts (a-c) requires a DSMB.

Data and Safety Monitoring Board

We will comprise a full Data and Safety Monitoring Board (DSMB), that will include three voting members from colleagues in the field. The PI on this grant is familiar with the implementation of a DSMB; he is currently serving as one of the board members of the NIDA Clinical Trials Network studies examining routine HIV testing among drug users.

The key elements of a DSMB include the following:

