- c. Assessment of adverse consequences: Several different research staff members will assess subjects in both the MMT and IPT interventions. For those on MMT who receive either HAART or TB Treatment, we will monitor for symptoms of opioid withdrawal. Alternatively, we will monitor for overdose in these subjects, diversion or drug interactions with MMT. We would also monitor for breaches of confidentiality in PT subjects. An initial investigation would be undertaken and simultaneously reported to the IRB using standard university procedures.
- d. Confidentiality of research data: Breaches of confidentiality regarding research data are more difficult to detect. For that reason, we have in place a number of safeguards including double-locked doors, locked file cabinets, confidential and dedicated fax machine and double password-protected computers. In accordance with federal and university policy, all research personnel are compliant with HIPAA training. If any breach of data confidentiality were detected, we would use similarly detailed procedures for report to the PI and IRB simultaneously.
- e. Complications from MMT: In this study, we will monitor for adverse consequences in a standard way. First, drug interactions between buprenorphine and HIV antiretrovirals have not been extensively evaluated. Efavirenz and nevirapine have been associated with reductions in methadone levels, and precipitated clinical withdrawal. In cases where we can detect symptoms of opiate withdrawal, we will increase the methadone dose to treat the symptoms of withdrawal. [name] was the first clinician to report cases of opiate withdrawal among patients receiving HAART and methadone and is currently investigating other pharmacokinetic interactions between methadone and buprenorphine with antiretroviral drug interactions. Methadone may

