For the FGDs, data will be analyzed qualitatively for themes as well as quantitatively for frequency of themes and relative rankings across all groups. This data will reveal some of the concerns and beliefs that patients have regarding MAT on presentation and their relative importance in treatment decision making.

SECTION VI: RESEARCH INVOLVING DRUGS, BIOLOGICS, RADIOTRACERS, PLACEBOS AND DEVICES

If this section (or one of its parts, A or B) is not applicable, state N/A and delete the rest of the section.

A. DRUGS, BIOLOGICS and RADIOTRACERS

1. Identification of Drug, Biologic or Radiotracer: What is (are) the name(s) of the drug(s) biologic(s) or radiotracer(s) being used? Identify whether FDA approval has been granted and for what indication(s).

Rifapentine and Isoniazid. Both are approved by the FDA.

Methadone is an FDA-approved medicine currently in Malaysia, and standard of care in Prison

B. DEVICES

1. Are there any investigational devices used or investigational procedures performed at Yale-New Haven Hospital (YNHH) (e.g., in the YNHH Operating Room or YNHH Heart and Vascular Center)? Yes No *If Yes, please be aware of the following requirements:*
NOT APPLICABLE

a

SECTION VII: RECRUITMENT/CONSENT AND ASSENT PROCEDURES**1. Targeted Enrollment: Give the number of subjects:**

a. targeted for enrollment at Yale for this protocol 80-120 per day will be recruited;
300-375 will be enrolled in parts b & c
b. If this is a multi-site study, give the total number of subjects targeted across all sites N/A

2. Indicate recruitment methods below. Attach copies of any recruitment materials that will be used.

 Flyers	 Internet/Web Postings	 Radio
 Posters	 Mass E-mail Solicitation	 Telephone
 Letter	 Departmental/Center Website	 Television
 Medical Record Review	 Departmental/Center Research Boards	 Newspaper
 Departmental/Center Newsletters	 Web-Based Clinical Trial Registries	
 YCCI Recruitment database	 Clinicaltrials.gov Registry (do not send materials to HIC)	
 Other (describe): Information sessions		

3. Recruitment Procedures:

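### The Part C liver stop names no drug, so for a participant on methadone and no TB drug it would, read literally, stop methadone

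*Combined protocol and SAP*

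**What the plan says.** Section V.10 (Minimizing Risks, Monitoring Adverse Side Effects) sets the rule for both trials together: in "Part B (trial of 26H vs 12HR) and Part C (MMT, vs. no MAT), patients will be seen monthly clinically for symptoms of hepatitis", and also for neuropathy, with LFT monitoring. Anyone above 5X ULN, or above 3X ULN with jaundice, nausea or fatigue, "will be stopped from receiving medications and LFTs will be monitored weekly to ensure that LFTs are decreasing". No drug is named, and there is no taper and no restart criterion. The LFT schedule that follows is by TB regimen: "LFTs will be measured at baseline and monthly for 3 months for 12HR and monthly x 6 months for 26H".

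Part C (V.3) is for prisoners with opioid use disorders "who are not or are currently being treated for TB and/or HIV". Its eligibility list reads "Has LTBI or active TB disease (based on screening in Part A), or no TB", and the 1c list in V.7 says the same in substance. The current arms are methadone and no MAT. Section VI.A lists rifapentine and isoniazid, and then: "Methadone is an FDA-approved medicine currently in Malaysia, and standard of care in Prison".

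Two other places deal with methadone under clinical stress. For a woman who becomes pregnant (V.7), "MMT will not be discontinued if she is receiving it as withdrawal has resulted in pre-term labor". Under Complications from MMT (V.11): "In cases where we can detect symptoms of opiate withdrawal, we will increase the methadone dose to treat the symptoms of withdrawal".

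**The concern.** For someone on 12HR, 26H or drugs for active TB, the rule has an obvious target. For a Part C participant on methadone and no TB drug it does not. The only drug from the Section VI.A list that this person takes is methadone, and ART would be the other candidate if the person is HIV-positive.

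The trigger is not remote. Part C admits AST or ALT up to 5X ULN, V.3 reports HCV antibody in 94% of HIV-positive and 63% of HIV-negative prisoners, and the lower limit needs only 3X ULN plus a symptom as common as nausea or fatigue.

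Staff who follow the sentence as printed would stop an opioid agonist abruptly, shortly before or after release from prison. That also takes away, in one arm only, the treatment that Part C sets out to compare. A no-TB participant has no TB treatment to complete. The loss would therefore fall mainly on the person's safety and on the monthly follow-up measures, not on the primary outcome.

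**Working it through.** **1. Which drugs can the rule reach?**

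| Part C participant | Drugs from the VI.A list being taken | What a literal stop removes |
|---|---|---|
| On 12HR or 26H, chose methadone | TB drug(s) and methadone | TB drug(s), and arguably methadone |
| No TB drug, chose methadone | methadone | methadone |
| No TB drug, chose no MAT | none | nothing |

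**2. Does the text limit the word to TB drugs?** The evidence points both ways.
- For a limit: the thresholds match those for rifapentine in V.9, and the LFT schedule names only 12HR and 26H.
- Against: the rule names Part C by its methadone comparison, it applies to anyone, and the next paragraph of V.10 uses the same word for what methadone patients are dispensed.
- No available sentence settles it. Part of V.11 was not in the text I had, and I claim nothing about it.

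**3. How many people?** Inputs are 25-50 per arm (V.3, Part C) and the estimates of 84% LTBI and 10-15% active TB (V.12, Part A). Assumption: those estimates hold in Part C.
- If LTBI and active TB are separate groups: 100 - 84 - 15 = 1%, up to 100 - 84 - 10 = 6%.
- If active TB lies within the 84%: 100 - 84 = 16%.
- Range in the methadone arm: 0.01 x 25 = 0.25 (about 0) to 0.16 x 50 = 8.

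Participants with untreated LTBI would add to this. Part B requires at least 6 months of sentence remaining and Part C at most 6. A person with LTBI and a short sentence can therefore generally enter Part C but not Part B, and V.3 says few prisoners with LTBI receive preventive therapy. The documents give no figure for this group. They also give no rate of crossing the LFT limits, so the number of events cannot be derived.

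**4. What would a stop do to the dose?** Inputs from V.3, Part C: start at 5 mg, add 5 mg each week, aim for at least 80 mg or an optimal dose, begin 3-4 months (13-17 weeks) before release.
- Time to 80 mg: (80 - 5) / 5 = 15 weekly steps = 15 weeks.
- No stop, 13 weeks available: 5 + 13 x 5 = 70 mg at release. With 17 weeks available, 80 mg is reached at week 15.
- Stop at week 4, restart the same day at 5 mg, 9 weeks left: 5 + 9 x 5 = 50 mg.
- The same with 13 weeks left: 5 + 13 x 5 = 70 mg.
- Loss at release: 70 - 50 = 20 mg, or 80 - 70 = 10 mg.

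Same-day restart is the favourable case, because the plan gives no restart rule.

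**5. Is a methadone stop consistent with the rest of the plan?** No. V.3, Part C says participants will be kept on medication-assisted treatment, with six months of care after release. V.10 makes no exception to match it.

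**The case against.** The strongest reply is that context already supplies the missing words. V.10 answers the risks set out in V.9, and V.9 ties liver injury to rifapentine and isoniazid. Methadone's listed problems there are drug interactions and withdrawal, and Complications from MMT in V.11 has no liver item. V.9 explains LFT monitoring by LTBI treatment in people with HCV. Methadone is described as routine care. Possible adverse drug experiences go to a licensed clinician (Section X.4). All of this stands, and it makes a TB-drug stop the probable intent. It does not amend a mandatory sentence that covers Part C and names no drug.

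The second reply is that the affected group may not exist. V.5 asks for more than 90 days of TB treatment remaining, V.12 adds being on TB medications, and the recruitment text in VII.3 describes Part C as LTBI or active TB. This is a real conflict and it lowers the certainty of the point. Even so, both formal eligibility lists admit people with no TB.

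A reader might also infer that the plan treats continued methadone as right whatever the liver tests show. The documents do not support that. The pregnancy exception rests on pre-term labor, the dose increase in V.11 answers withdrawal, and nothing shows that continuing methadone above 5X ULN is preferable. The argument here is for a clinical decision in place of an automatic one.

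**Conclusion.** The point holds as a gap in wording with a safety consequence. V.10, read literally, stops methadone in a Part C participant on no TB drug, without taper or restart rule, and this contradicts the commitment in V.3 to maintain treatment. It does not show that the investigators mean to stop methadone.

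The size is small and uncertain: about 0-8 people in the methadone arm if the Part A rates carry over, plus an unknown number with untreated LTBI, of whom an unknown fraction would cross the limits.

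Two stronger readings are tempting and should not be drawn:
- That every stop costs 15 weeks of re-titration. This applies only to someone already at 80 mg. The week-4 example costs 10-20 mg at release. It assumes the V.3 starting schedule, and V.9 allows rises of 5, 10 or 20 mg a day for withdrawal in people already on OAT, without saying whether that covers a restart.
- That people on drugs for active TB have no LFT interval. V.10 already sets monthly visits with LFT monitoring for Part C, and monthly is the ordinary reading.

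**What to change.** In V.10, change *medications* in the stopping sentence to *TB medications (isoniazid, rifapentine or drugs for active TB)* and add: *Methadone and ART are not stopped automatically under this rule; the treating physician reviews them.*

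The cost is one phrase and one sentence. The stop stays mandatory for every TB drug, and no visits or blood draws are added. The downside is that methadone and ART decisions then rest on physician review instead of an automatic stop.

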- 1) Selecting experts in the field (HIV, TB, Substance abuse) who will serve as members of the board. If funded, we will select two U.S. and one Malaysian experts to serve on the DSMB. As in other NIDA trials, we will work with NIDA staff to select these individuals. Individuals from NIDA will be responsible for the final invitation to participate on the Board. During the first six months of the study, while final implementation is being conducted, the DSMB will convene to go over their charge, examine the guidance set forth by the study team and to question the PI and biostatisticians about pre-defined endpoints. Once these outcomes and stopping rules are defined, the Board will reconvene at regularly scheduled times to assess outcomes.

Defining stopping rules. For Aim 1, part B, we will be examining completion and tolerability of two LTBI prevention strategies. The study is not powered to reduce development of active TB, but to establish safety in prisoners who have high prevalence of HCV infection. Tolerability (discontinuation from study medication) will be the primary outcome. All discontinuations will be reviewed by the PI and the team. Death will be brought to the DSMB within 24 hours if medication related (though most deaths are related to TB itself). If the discontinuation rate is 3-fold higher in either group, either in the interim analysis when 50% is enrolled or at any time within study assessment, the study will be stopped for safety purposes and a press release will be made. For Part B, we anticipate a difference between the control group and the two intervention groups of about 40%.

- 2)
- 3) Assessment of possible adverse consequences of the various interventions. No specific guidance is available for DSMBs for these kinds of interventions; however, we have considerable experience with CHRP, Project PLUS, Project TRUST, Project CONNECT, Project BEST and other community research studies to provide a specific plan. In fact, in order to collect information about the "safety" of the intervention, we intend to hire a research assistant to gather safety information from three independent sources. These include the weekly study meeting where all active participants are discussed, daily conversations with the Health Educators and weekly conversations with the subject

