
Part B: In CDC's original non-inferiority trial of 26H v 12HR, treatment completion differed significantly (67.0% v 82.1%); however, there were no HIV+s (and therefore no ART prescribed)

and HCV infection was <3%. Therefore tolerability for a longer exposure to 26H may decrease completion further. We will compare the proportion completing TB preventive therapy (no adverse side effects) for the two groups and control for any confounders that may differ after randomization. Using an alpha=0.05 and power=0.8 and a 20% difference (most conservative), we would need 118 per arm. We hypothesize, however, that 26H will be tolerated even less based on studies of IPT hepatotoxicity in a RCT of isoniazid in prisoners (21% in with HCV)⁴² and HCV+ patients (correlated with longer IPT exposure).⁴³⁻⁴⁵ Thus, even increasing the difference in treatment completion to 20% (still conservative), the sample size would need to be 164. Thus, we will conservatively enroll 177 per arm or 354 patients total. We will analyze the data two ways, including ITT as a difference in proportion of treatment completion used in RCTs. In order to discern factors associated with differences in treatment completion, we will treat the entire recruited sample as a cohort and using Cox regression, examine time to treatment discontinuation between the two groups using Cox Proportion Hazards as well as examine the independent factors associated with treatment discontinuation (e.g., being on ART, HCV status, baseline AST/ALT, CD4 strata, etc).

Part C: Eligibility will be having no TB disease, TB disease or LTBI, on TB medications that must be completed after release, and meet pre-incarceration DSM-V criteria for opioid dependence. We will compare a control group of prisoners choosing no OAT and compare them to OAT patients. Even though we anticipate 15-20% attrition, we will count missing=failure to be conservative and will censor the data based on the mid-point between the last and the missed visit. The primary outcome will be the proportion completing treatment for active or LTBI. Secondary analyses will compare Kaplan Meier curves using Cox proportion hazards and time to discontinuation. TB treatment adherence will also be measured using MEMS caps and analyzed as we have done previously in TB patients in Ukraine.

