f. Who will have access to the protected health information (such as the research sponsor, the investigator, the research staff, all research monitors, FDA, Yale Cancer Center Data and Safety Monitoring Committee (DSMC), SSC, etc.)? (please distinguish between PHI and de-identified data)

The Principal Investigator and research staff will have access to collected data.

g. If appropriate, has a [Certificate of Confidentiality](#) been obtained? The research is covered by a CoC since it is NIH-funded.

h. Are any of the study procedures likely to yield information subject to mandatory reporting requirements? (e.g. HIV testing – reporting of communicable diseases; parent interview -incidents of child abuse, elderly abuse, etc.). Please verify to whom such instances will need to be reported.

We plan to report any infectious disease we identify (eg, HIV, TB) to the local authorities in accordance with the local reporting requirements.

SECTION IX: POTENTIAL BENEFITS

Potential Benefits: Identify any benefits that may be reasonably expected to result from the research, either to the subject(s) or to society at large. (Payment of subjects is not considered a benefit in this context of the risk benefit assessment.)

The benefits for AIM 1 are numerous. For Part A, identifying the optimal TB screening strategy for prisoners, will guide prison care worldwide, but especially in LMICs. For Part B, the potential benefits are that we may identify that providing a SHORT-COURSE INH/RIFAPENTINE (12HR) course results in INCREASED LTBI completion rates and LOWER or even SIMILAR toxicity. As such, it would greatly improve LTBI treatment strategies for HIV+ prisoners who are at profoundly high risk for developing active TB. For Part C, the benefits of participating in this study include being better informed about available medication-assisted treatment options, receiving a medication-assisted treatment of their choice to manage their opioid use disorder, and receiving healthcare for TB management.

SECTION X: RESEARCH ALTERNATIVES AND ECONOMIC CONSIDERATIONS

1. **Alternatives:** What other alternatives are available to the study subjects outside of the research?

The alternative to participation in the study is non-participation. Subjects who do not wish to participate in this study may obtain healthcare, drug treatment, and other services through standard means in the prison.

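### Part B is about safety where HCV is common, but no planned analysis compares hepatotoxicity by arm or compares the arms within HCV strata

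*Combined protocol and SAP*

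**What the plan says.** **Purpose.** The stopping-rules paragraph of Section V.11 says of Part B: "The study is not powered to reduce development of active TB, but to establish safety in prisoners who have high prevalence of HCV infection". It continues: "Tolerability (discontinuation from study medication) will be the primary outcome". Section V.3, Part B, raises possible extra liver damage from the two-drug regimen in people with chronic HCV as the open question. It asks for completion and tolerability to be assessed together. Section IX hopes to find that 12HR "results in INCREASED LTBI completion rates and LOWER or even SIMILAR toxicity".

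**Design.** Section V.3 lists HCV antibody status among four stratification factors.

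**Analysis.** Section V.12, Part B, says "We will compare the proportion completing TB preventive therapy (no adverse side effects) for the two groups", by intention to treat. It then plans a Cox model of time to discontinuation between the arms. To look for predictors, "we will treat the entire recruited sample as a cohort"; HCV status is one example, next to ART, baseline AST/ALT and CD4 stratum. The section names no liver endpoint, no AST/ALT comparison by arm, no contrast within an HCV stratum and no interaction term.

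**Measurement.** Section V.10 says "LFTs will be measured at baseline and monthly for 3 months for 12HR and monthly x 6 months for 26H". Section V.3 gives the same 4-weekly interval.

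**The concern.** The liver question is put clearly, the stratification suits it and the data will be collected, but the analysis section does not use them for it. Someone following Section V.12 as written would finish with two arm contrasts on staying on treatment and one hazard ratio for HCV averaged over both arms. None of these is an estimate of how often 12HR injures the liver compared with 26H, overall or in HCV-positive prisoners.

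Two errors could follow. The pooled HCV coefficient could be read as evidence about 12HR, which it is not. And if liver results were added after the data were seen, the choice of event definition and time window would be open, although the arms are followed for different lengths of time.

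**Working it through.** **1. The plan's own figures.** Section V.12 sizes Part B on completion: 118 per arm, then 164, then 177 enrolled per arm. An absolute 20-point difference never needs more than 97 per arm at 80% power and alpha 0.05 (107 with continuity correction). A relative 20% increase on 69.0%, to 82.8%, gives 118 (one-sided, uncorrected) and 164 (two-sided, corrected). The documents state neither that reading nor the sidedness. No size, power or precision is given for hepatotoxicity, so I take 177 per arm as fixed.

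**2. What the planned outcomes capture.**
- Included: liver events that force a stop under Section V.10 (over 5x ULN, or over 3x with symptoms).
- Mixed in: refusal and pregnancy (Section V.3, reasons for stopping) and release, which Section V.3 names with hepatotoxicity as a main cause of non-completion.
- Missed: enzyme rises that do not reach the stopping limit.

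**3. What the Cox HCV term estimates.** With main effects only, log hazard = baseline + b1(arm) + b2(HCV). Here b2 is the effect of HCV averaged over both arms, and b1 is forced to be the same in HCV-positive and HCV-negative people. Whether the arm effect differs by HCV status needs a third term, b3(arm x HCV), or separate contrasts by stratum.

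**4. Stratum sizes.** Section V.3 gives HCV prevalence of 94% in HIV-positive and 63% in HIV-negative prisoners. The HIV mix of Part B is not stated. Half is an assumption, suggested by the 250 + 250 planned for Part A.
- Half HIV-positive: 0.5(0.94) + 0.5(0.63) = 0.785; 0.785 x 177 = 139 HCV-positive and 38 HCV-negative per arm.
- None HIV-positive: 0.63 x 177 = 112 and 65.
- All HIV-positive: 0.94 x 177 = 166 and 11.

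**5. Precision.** Section V.12 cites 21% hepatotoxicity on isoniazid with HCV. Setting both arms at 21% (assumption), half-width = 1.96 x sqrt(2 x 0.21 x 0.79 / n).

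| Stratum | n per arm | Half-width (points) |
|---|---|---|
| HCV-positive | 112 / 139 / 166 | 10.7 / 9.6 / 8.8 |
| HCV-negative | 11 / 38 / 65 | 34 / 18 / 14 |

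The normal approximation is crude at 11 per arm. For the interaction at 139 and 38 per arm: 1.96 x sqrt(0.3318/139 + 0.3318/38) = 0.207, or about 21 points.

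**6. Power in HCV-positives** (139 per arm, two-sided 5%, pooled normal approximation, 12HR rates assumed).
- 21% v 10%: (0.110 - 1.96 x 0.0434) / 0.0429 = 0.58, power about 72%.
- 21% v 15%: (0.060 - 1.96 x 0.0461) / 0.0459 = -0.66, power about 25%.

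**7. Follow-up.** Both arms are drawn 4-weekly on treatment: 12/4 = 3 draws on 12HR, and 6 full intervals within 26 weeks on 26H, each after a baseline draw. The counts differ because the regimens differ in length. A cumulative proportion over the whole course therefore combines drug effect with length of exposure and observation.

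**The case against.** The strongest reply is that safety is already compared by arm. Section V.11 makes discontinuation the primary outcome, and liver values over the limit stop treatment, so serious liver events count. Section V.12 attaches a condition about adverse effects to completion. On step 4, about 79% of participants would be HCV-positive, so the overall arm contrast largely describes them. Much of this stands. A reader might infer that the trial cannot support any conclusion on toxicity; the documents do not bear that out. What remains is that the outcome is mixed, the adverse-effect condition is undefined, and stops for other reasons could create or hide an arm difference.

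A reader might also infer that 12HR is watched half as closely. It is not: the interval is the same and only the duration differs. Whole-course toxicity is a legitimate comparison of two regimens, and part of any excess on 26H would be real extra exposure. Section V.9 notes that isoniazid hepatitis can appear after many months, so a 12-week window alone would favour 26H.

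Nor do the documents say that Part B concerns HCV-positive prisoners only, or that HCV was chosen as a stratum for this analysis. The stated target is a prison population where HCV is common, and no reason is given for any stratum. The Section IX sentence is a hope about HIV-positive prisoners, not a planned claim.

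Part of Section V.11 was not available to read. The absence is asserted for Section V.12, Part B, which was.

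**Conclusion.** The point holds as a cheap improvement. Section V.12 lacks a hepatotoxicity contrast by randomised arm and any arm contrast within the HCV strata, and the pooled HCV term does not stand in for either. The completion and discontinuation analyses remain valid for what they measure.

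The likely gain is an HCV-positive estimate with a half-width of roughly 9 to 11 points, given 177 per arm, the protocol's HCV prevalences and a 21% event rate in both arms. That could show a large difference. It would not establish that the regimens are similar: no margin is stated, and power for 21% v 15% is only about a quarter. The HCV-negative and interaction results would be descriptive.

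**What to change.** First reconcile two sets of statements, because they decide who counts as an event and when it can be seen:
- stopping criteria: Section V.3, Part B (Grade 4 toxicity) against Section V.10 (ULN multiples and Grade 3 neuropathy);
- liver-test schedule: the rifapentine monitoring text in Section V.9 (baseline only) against Sections V.3 and V.10 (monthly).

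Then add to Section V.12, Part B:
1. A secondary comparison of hepatotoxicity by randomised arm, from the liver tests already planned. Define the event relative to baseline, since entry allows AST/ALT up to 5x ULN and a fixed threshold would mix existing disease with drug effect.
2. That result, and completion and discontinuation, reported overall and in HCV-positive and HCV-negative strata, with 95% confidence intervals and an arm-by-HCV interaction. Label the HCV-negative and interaction results descriptive.
3. Two windows side by side: the first 12 weeks, with three post-baseline draws scheduled in each arm, and the whole course with the number of draws, or an exposure-time analysis. Neither should stand alone.
4. A sentence saying that the pooled Cox term for HCV does not answer whether 12HR does better or worse than 26H in HCV-positive prisoners.

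The cost is analysis-plan wording and some extra tables, with no new participants or tests. The drawback is imprecision in the smaller stratum, which the intervals will show.
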